1.1 Trial Registration

1.1.1 Registry

Registered in ClinicalTrials.gov with reference number: NCT04188314.

Submitted protocol to National Health Research Database (NHRD) – awaiting feedback.

1.1.2 WHO Data Set

Data category	Information
Primary registry and trial identifying number	ClinicalTrials.gov: NCT04188314
Date of registration in primary registry	4 December 2019
Secondary identifying numbers	SAHPRA Phase IV Notification: N20210205
Source(s) of monetary or material support	JPRF Research Fund
Primary sponsor	JPRF Research Fund
Secondary sponsor(s)	Abbvie Scholarship
Contact for public queries	[name]: [contact]
Contact for scientific queries	[name]: [contact]
Public title	Comparing Quality of Recovery Between Desflurane & Isoflurane in Eye Surgery Patients at [name] Academic Hospital (DIQoR Trial)
Scientific title	A Randomised Control Trial to Compare Quality of Recovery between Desflurane and Isoflurane Inhalational Anaesthesia in Patients Receiving General Anaesthesia for Ophthalmological Surgery at [name] Academic Hospital (DIQoR Trial)
Countries of recruitment	South Africa
Health condition(s) or problem(s) studied	Quality of Recovery after General Anaesthesia
Intervention(s)	Control drug: Isoflurane Intervention drug: Desflurane
Key inclusion and exclusion criteria	Ages eligible for study: 18-80 years Sexes eligible for study: both Accepts healthy volunteers: no Inclusion criteria: adult patients (18-80 years), patients presenting for ophthalmological surgery under general anaesthesia, ASA I and II, able to communicate in English, Setswana or Afrikaans.

Data category	Information
	Exclusion criteria: ASA III and above, contra-indications to Laryngeal Mask Airway use during general anaesthesia, severe medical or surgical conditions who are expected to have prolonged admissions or ICU admissions, uncontrolled psychiatric conditions, known allergy or adverse reaction to volatile anaesthetics, known or suspected susceptibility to Malignant Hyperthermia, incomplete records, patients who are not treated according to the prescribed treatment protocol.
Study type	Interventional Allocation: randomised Masking: double blind (patient and observer)
Date of first enrolment	February 2020
Target sample size	180
Recruitment status	Recruiting
Primary outcome(s)	To evaluate whether there is a difference between post-operative quality of recovery in patients who received desflurane and in patients who received isoflurane for maintenance of anaesthesia, using the QoR-15 score, a patient-rated outcome measure.
Key secondary outcomes	
 To compare the consumption and relative cost of using isoflurane vs desflurane with a minimal or basal flow anaesthetic technique. To evaluate the difference in time spent in the recovery room between the two patient groups will also be compared.

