3.2.2 Eligibility Criteria

Inclusion Criteria:

- Adult patients between the ages of 18-80 years of age.
- Patients presenting for ophthalmological surgery under general anaesthesia.
- ASA I and II.
- Able to communicate in English, Setswana or Afrikaans.

Exclusion Criteria:

- Patients outside the specified age range.
- ASA III and above.
- Patients with contra-indications to Laryngeal Mask Airway use during general anaesthesia.
- Patients with severe medical or surgical conditions, who are expected to have prolonged admissions or ICU admissions.
- Patients with uncontrolled psychiatric conditions like depression, schizophrenia, mania, dementia.
- Patients with known allergy or adverse reaction to volatile anaesthetics.
- Patients with known or suspected susceptibility to Malignant Hyperthermia.
- Patients with incomplete records (Data Collection Form and QoR-15).

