- Treating anaesthetist to test the machine daily, as per standard practice, with a clean circuit. Carbon dioxide absorber should be checked daily and replaced when needed. The treating anaesthetist will record the machine leak as determined during the machine check.
- Allow fresh gas flow of 0.2-0.5 l/min, aiming to reduce the fresh gas flow as low as possible, taking into consideration the machine leak. This change allows the treating anaesthetist to adjust the fresh gas flow according to the amount of leak in the circuit. All responding anaesthetists felt more comfortable with this adjustment to the protocol.
- Steps to take when the bellows collapse: increase the fresh gas flow to 2 l/min and increase the concentration on the vaporiser to maintain 1MAC (maximum 12% for Desflurane). This will prevent a decrease in the MAC from flushing the circuit with oxygen only.
- In some cases, a small dose of muscle relaxant may be used to facilitate immobility during the procedure. The dose of muscle relaxant will be limited to 25% of the intubating dose, and reversal with neostigmine (plus glycopyrrolate or atropine) is mandatory. Glycopyrrolate is preferred, but it is currently out of stock.

This small dose of muscle relaxant should not affect the patient's post-operative quality of recovery, especially if it is reversed.

- Dose of Fentanyl changed to 1.5-3mcg/kg, to allow for smaller doses to be given for short procedures lasting 30 minutes or less.
- In cases where post-operative pain is expected, the treating anaesthetist may administer 50-100mg Tramadol 20 minutes before the end of the procedure, rather than waiting until the patient was in the recovery room.
- The anaesthetic workstation in the ophthalmology theatre has been changed to a Datex-Ohmeda CS2, which gives a clear indication of the amount of circuit leak after the machine check, and experience has shown that it has a smaller baseline leak than the Drager Perseus workstation.

The changes made to the standardised anaesthesia treatment protocol makes it more practical and pragmatic, and it will improve adherence to the study protocol. This will prevent exclusion of cases which were not treated according to the study protocol.

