3.3.2 Blinding

The patient will be blinded to the group they have been randomised to, as the vapour will only be started after induction of anaesthesia. The research assistant administering the post-operative QoR-15 will be blinded to the intervention.

The treating anaesthetist, the Chief Researcher and theatre staff will not be blinded to the intervention, as this would not be practical. All treating anaesthetists and theatre staff will be strongly inculcated not to disclose the allocation status of the participant at any time prior or after the general anaesthetic.

The piece of paper indicating the group will be attached to the Case Report Form. The Case Report Form will be collected by the Chief Researcher and will not be in the patient's file where it may unblind the patient or research assistant.

There are no circumstances under which unblinding will be permissible.

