3.4.3 Data Collection Procedures

Patients will be assessed by the chief researcher pre-operatively on the day before surgery. The demographic information on the Data Collection Form (Section A) will be completed. Information will be obtained from the patient's file, as well as from an interview with the patient. The chief researcher will accurately measure the patient's weight and height with the available scales and measuring devices in the wards.

Patients will then be asked to complete the QoR-15 in the language of their choice, as a measure of health status over the previous 24 hours. Where possible, the QoR-15 form will be handed to the patient to complete by themselves. However, in cases where patients are visually impaired, the items on the questionnaire will be read to them, and their responses recorded.

The following day, the treating anaesthetist will complete the information about the procedure in Section B of the Data Collection Form: anaesthetic time, amount of vapour used, additional medication administered, recovery time, any adverse events (bronchospasm, laryngospasm, post-operative nausea and vomiting and/or other), and whether the prescribed anaesthetic protocol was followed.

Post-operatively, a blinded observer (research assistant) will review the patient on the day following their surgery, prior to discharge. The patients will complete the QoR-15 again.

As follow-up will be done before discharge, retention of patients to follow-up should not present any difficulties.

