3.8 Reliability and Validity

- Validity:
 - Internal validity should be assured on the basis that the anaesthetic techniques will be unchanged between the two groups, except for the anaesthetic vapour. Maintaining the end-tidal vapour concentration at 1MAC for both drugs will prevent disproportionate effects of one drug over the other. The patient population should be homogenous, as only ASA I and II patients presenting for ophthalmological surgery will be included in the study.
 - The chief researcher will counsel each treating anaesthetist prior to them starting a study case to ensure that they follow the required standardised anaesthesia protocol. This will reduce the

chance of protocol violations occurring. Any deviations from the standardised protocol will be recorded on the Data Collection Form and will be assessed by the chief researcher.

- Construct and content validity are assured on the basis that the QoR-15 has been extensively validated in many different languages and for many different surgery types.
- Data on the Case Report Forms will be inspected for completeness as per section 4.3.5. Incomplete cases will be excluded from analysis.

- Reliability:

- The QoR-15 is a reliable tool to use. During development of the tool, the internal consistency was measured using Cronbach α and split-half reliability, both of which had satisfactory results.
- Reproducibility of the QoR-15 was excellent, and exceeded that reported for the QoR-40, indicating that the QoR-15 score can be interpreted with confidence.

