6.7 Case Report Form: Data Collection

Case Report Form: Data Collection				
Date: ___ / ___ / ___		Study #: _____		
SECTION A: PATIENT INFORMATION:				
Age:	years			
Gender:	Male	Female		
Weight:	kg	Height:	m	BMI: _____
ASA Status:	I	II	III	IV
Risk for PONV:	Female	Previous PONV	Motion Sickness	Non-smoker
Smoking History:	Non-smoker	Ex-smoker	Current Smoker	Pack years: _____
Comorbidities:	None	Hypertension	Diabetes	Pulmonary Disease
	Cerebrovascular Disease	Renal Disease	HIV	Cardiovascular Disease Psychiatric Conditions Other (Specify below)
If Other, Details of Condition: _____				
Any Anaesthesia in the Past Month?		Yes	No	
If YES:		General	Regional	Local Infiltration
Any Complications?		Yes	No	
If YES, Describe: _____				
SECTION B: INFORMATION ABOUT PROCEDURE:				
Group:	Desflurane	Isoflurane		
Intravenous Induction Time:	End of Anaesthesia: _____			
Time Vapour Started:	Time Vapour Stopped: _____			
Millilitres of Vapour Used:	ml			
Propofol at Induction:	mg			
Fentanyl at Induction:	mcg			
Intra-op Propofol Top-up:	No	Yes →	Number of top-ups given: _____ Total top-up dose: _____ mg	
Intra-op Fentanyl Top-up:	No	Yes →	Number of top-ups given: _____ Total top-up dose: _____ mcg	
Intra-op Muscle Relax. Top-up:	No	Yes →	Number of top-ups given: _____ Total top-up dose: _____ mg	
Neostigmine given:	No	Yes →	Time: _____ Dose: _____ mg	
Atropine / Glycopyrrolate given:	No	Yes →	Time: _____ Dose: _____ mg	
Intra- or Post-op Tramadol:	No	Yes →	Time: _____ Dose: _____ mg	
Post-Op Ondansetron:	No	Yes →	Time: _____ Dose: _____ mg	
Post-Op Metoclopramide:	No	Yes →	Time: _____ Dose: _____ mg	
Adverse events:	Bronchospasm	Laryngospasm	Nausea / Vomiting	Other (specify below)
Please inform [name] immediately of any adverse events ([name])				
Time into Recovery:			Time out of Recovery: _____	
Anaesthesia administered as per study protocol:			Yes	No
If no, please describe modification: _____				
[name]; MMed Research; Feb 2020			DIQoR Trial	

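### Patients with a valid day-1 QoR-15 can be dropped after randomisation for a protocol deviation or an unrelated blank field, and no analysis set is defined

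*Combined protocol and SAP*

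**What the plan says.** All references are to the combined protocol and SAP.

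**Exclusions**
- Section 1.1.2 lists among the exclusion criteria "incomplete records, patients who are not treated according to the prescribed treatment protocol".
- Section 3.2.2 excludes "Patients with incomplete records (Data Collection Form and QoR-15", but does not list deviators.
- Section 3.8 has the Case Report Forms checked for completeness, then says "Incomplete cases will be excluded from analysis". Section 3.4.2 defines those forms as the Data Collection Form and both QoR-15 forms.
- Section 3.2.5 says of the revised anaesthesia protocol: "This will prevent exclusion of cases which were not treated according to the study protocol".

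**Who judges deviations**
- Section 3.4.3 has the treating anaesthetist record "whether the prescribed anaesthetic protocol was followed". The form in 6.7 gives a yes/no box and the prompt "If no, please describe modification".
- Section 3.8 continues: "Any deviations from the standardised protocol will be recorded on the Data Collection Form and will be assessed by the chief researcher".
- Section 3.3.2 states: "The treating anaesthetist, the Chief Researcher and theatre staff will not be blinded to the intervention".

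**Analysis**
- Section 3.6 tests the post-operative QoR-15 between groups. It names no analysis set and no method for missing data.
- SPIRIT item 20c in 6.1 (analysis population and missing data) is marked not applicable.

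**The concern.** Randomisation makes the two arms comparable as allocated. Removing patients for events after allocation gives up that protection unless the removals are unrelated to arm and outcome. Here the rules allow removal of a patient whose primary outcome is known and valid, for one of two reasons: the anaesthetic departed from protocol, or a field that the primary test does not use was left blank. Those who flag and assess deviations know the arm, and nothing says which deviation disqualifies.

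Bias follows if the rate of exclusion, or the kind of patient excluded, differs by arm. Equal rates alone do not prevent it. Because the sections disagree on deviators, two analysts could also build different primary datasets from the same protocol.

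**Working it through.** **1. The rules side by side**

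| Section | Deviators | Incomplete records |
|---|---|---|
| 1.1.2 | excluded | excluded |
| 3.2.2 | not mentioned | excluded (Data Collection Form and QoR-15) |
| 3.2.5 | exclusion presumed | – |
| 3.8 | recorded and assessed, no consequence stated | excluded from analysis |
| 3.6 | silent | silent |

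No section says deviators are kept.

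**2. What the primary test needs**

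It needs the arm and the day-1 QoR-15. Section B of the form in 6.7 also holds induction doses, millilitres of vapour and recovery-room times. Section 3.5.3 lists back-up sources for missing medication, anaesthesia times, vapour times and vapour volume. Recovery-room times are not on that list, although 3.4.1 names the nursing theatre record as holding them. No exception is made for fields the primary test does not use.

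**3. Timing and knowledge**

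Under 6.6 the form is handed in at the end of the procedure or left in the recovery room, so the anaesthetist's flag precedes the day-1 score. The timing of the Chief Researcher's assessment is not given. The Chief Researcher also monitors completed documents and database entries (3.7.1) and stores each patient's documents together (3.5.2). Nothing stated prevents the assessment being made with the score known.

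**4. The plan's own figure**

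Inputs from 3.2.8: difference 8, SD 18.5, two-sided 5%, 85 per arm. The noncentral t gives 80.0% power at 85 per arm and 79.6% at 84. The figure reproduces and has no reserve.

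**5. Bias from exclusion (illustration)**

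The documents give no exclusion rates and no scores for excluded patients, so these are assumed, with no true difference between arms. Let f be the fraction excluded from an arm and g the points by which those excluded score below that arm's full mean. The retained mean rises by f·g/(1−f), so

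bias = f₁g₁/(1−f₁) − f₀g₀/(1−f₀), and SE = 18.5·√(1/n₁ + 1/n₀) with n = 85(1−f).

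For example, with f₁ = 0.15, f₀ = 0.05 and g = 10 in both arms:
- bias = 0.15×10/0.85 − 0.05×10/0.95 = 1.765 − 0.526 = 1.24
- n = 72.25 and 80.75, so SE = 2.996
- bias/SE = 0.413, and the two-sided normal rejection probability is 7.0%.

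| f₁ / f₀ | g₁ / g₀ | Bias (points) | SE | Type I error |
|---|---|---|---|---|
| 10% / 5% | 5 / 5 | 0.29 | 2.952 | 5.1% |
| 15% / 5% | 10 / 10 | 1.24 | 2.996 | 7.0% |
| 15% / 5% | 18.5 / 18.5 | 2.29 | 2.996 | 11.9% |
| 10% / 10% | 10 / 0 | 1.11 | 2.991 | 6.6% |
| 10% / 10% | 10 / 10 | 0 | 2.991 | 5.0% |

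Against the MCID of 8, 1.24 points is about 15% and 1.11 is about 14%. The third row is an extreme case. The sign reverses if the arms are swapped.

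**6. Power when rate and kind match across arms**

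| Excluded | Power from 170 (n per arm) | Power from 180 (n per arm) |
|---|---|---|
| 5% | 78.0% (80.75) | 80.3% (85.5) |
| 10% | 75.7% (76.5) | 78.1% (81) |
| 15% | 73.3% (72.25) | 75.7% (76.5) |

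Section 3.2.8 gives 170 with no allowance for losses. Section 1.1.2 gives a target of 180. If 180 are randomised, 170 remain after 10/180 = 5.6% are excluded.

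**The case against.** **The deviator rule is thinly based.** It is explicit only in the registry-style table of 1.1.2 and presumed in one sentence of 3.2.5; the main eligibility section omits it. This shows an inconsistency and not a settled per-protocol analysis. That is fair, but 1.1.2 is part of this protocol and no section retains deviators. The incomplete-records exclusion stands separately in 3.2.2 and 3.8.

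**The blank-field reading is too broad.** Only 3.2.2 names both forms, and it joins them with *and*. However, 3.8 applies completeness to the Case Report Forms, which 3.4.2 defines to include the Data Collection Form, so the reading holds.

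**There are real safeguards.** Section 3.2.5 widened the anaesthesia protocol, and propofol and fentanyl top-ups fall within it. Each anaesthetist is counselled before a study case. Section 3.5.3 provides back-up sources. The blinded research assistant checks the day-1 form at the bedside and enters the data. The completed Data Collection Form is kept apart from the QoR-15 forms when it is handed in. All this should reduce exclusions and makes an informed judgement of deviations less likely. None of it removes the rule or fixes when the assessment is made.

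**The magnitude is assumed.** This stands. The mildest differential scenario is negligible, and nothing shows that the larger ones will occur.

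**Keeping deviators can cost power.** This stands in part. Suppose 10% or 15% in each arm deviate and contribute no between-arm difference at all. The expected difference becomes 8×0.90 = 7.2 or 8×0.85 = 6.8, and power at 85 per arm is 71.3% or 66.4%. Excluding the same fractions leaves 75.7% or 73.3%. That assumption is extreme. The loss is a reason to prevent deviations; it does not justify selecting patients after randomisation. The only adherence data are from the non-randomised pilot in 3.2.5, where 2 of 12 cases received sevoflurane.

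**Conclusion.** The concern holds and must be fixed. The stated rules permit exclusion from the primary comparison on post-randomisation events, with deviations judged by people who know the arm and without a criterion, and section 3.6 does not override them. This is an error in the rules as written as well as a missing detail.

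That conclusion rests on the text and not on the illustrative numbers. The actual bias is unknown in size and direction, and the documents do not show that it will occur. It could be negligible if few patients are excluded. The figures assume an SD of 18.5, 85 per arm, no true difference for the type I error results, and the exclusion rates and scores shown.

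**What to change.** 1. Delete the deviation and incomplete-records items from the exclusion criteria in 1.1.2, and the incomplete-records item in 3.2.2. Update the registry entry if it carries them.
2. Add to 3.6: *The primary analysis includes every randomised patient with a day-1 QoR-15 score, in the arm to which they were randomised, regardless of adherence or of missing data in other fields; a missing field affects only the analyses that use it.*
3. Replace the 3.8 sentence that removes incomplete cases with: *Missing data are handled as stated in 3.6.*
4. Align 3.2.5 and SPIRIT item 20c with this.
5. Report missing day-1 scores by arm, with reasons. In the pilot, two of the first four patients had been discharged before the post-operative visit; the plan has since assigned a research assistant to that visit. A sensitivity analysis for missing scores is optional.
6. Any per-protocol analysis would be new and for sensitivity only. Its deviation criteria should be set before the data are analysed, and deviations classified without knowledge of the QoR-15 score.

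**Cost:** wording in six places (1.1.2, 3.2.2, 3.2.5, 3.6, 3.8 and SPIRIT 20c), possibly the registry entry, one table, and the committee notification already foreseen in section 4. No new data are collected. The downside is dilution of the effect if many patients deviate: probably slight if deviations are few, larger in the extreme case shown above.

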1.2 Revision Chronology

Date	Protocol Amendment Number	Description
1 Nov 2018	1	Original
8 April 2019	2	Amendments after first review by SMU School Research Committee, formatted according to SPIRIT Statement 2013. Change in title and development of acronym.
14 Feb 2020	3	Updated Standard Anaesthesia Treatment Protocol, Updated Case Report Form: Data Collection, Included results from

		Feasibility Questionnaire and Pilot Study. Included details of registration with ClinicalTrials.gov.
10 Oct 2020	4	Updated title: Removed “[name] Academic Hospital”, replaced with “a Tertiary Hospital”. This was requested by the SMU Research Ethics Committee to make the research more generalizable.
19 April 2021	5	Added SAHRA reference number for notification of Phase IV trial. Adjusted time-line, which has been affected severely by the COVID-19 pandemic.

1.4 Funding

- Expenses = **R 51 037**:
 - Statistician fee (including: data plan, data analysis and randomisation service): R 5 000
 - Desflurane (6 bottles): R 9 537 (incl. VAT)
 - Translation costs: R 3 500
 - Printing costs: R 3 000
 - Research assistant: a research assistant will be paid R100 per hour to visit the patient post-operatively in order to complete the QoR, as well as to read the data into REDCap.
 - Estimated 2 hours per day, 25 days per month, for 6 months = R30 000
- Income:
 - Abbvie Scholarship: **R 10 000**
 - The chief researcher is a current recipient of the Abbvie Scholarship.
 - JPRF application: **R50 000**

- The chief researcher was successful in the application for funding from the SASA Jan Pretorius Research Fund. (Grants are made to deserving members of SASA for clearly defined research projects, which are acceptable to SASA and fall within the scope of Anaesthesia.)

1.5 Timeline

8 November 2018	Submission to School Research Committee
April 2019	Submission of revised protocol to School Research Committee
July 2019	Submission to SMU Research Ethics Committee
October 2019	Approval obtained from SMUREC: SMUREC/M/240/2019:PG
December 2019	Trial registered with ClinicalTrials.gov: NCT04188314
January- February 2020	Pilot Study (10 patients)
Early February 2020	Review results of pilot study
February 2020	Start data collection
March 2020	Covid-19 Pandemic starts
October 2020	Data collection resumes
July 2021	End data collection
August 2021	Analyse data
September 2021	Write dissertation and article for publication
October 2021	Submit dissertation for evaluation

2 Introduction

